3.13.1 Adverse Events

AEs will be coded using the MedDRA dictionary (Version 20.0). Treatment-emergent AEs (TEAEs) are any AE occurring or worsening in severity after the first administration of study medication. All AEs (including SAEs) will be graded using the 5-point Common Terminology Criteria for Adverse Events (CTCAE) V5.0 scale (mild, moderate, severe, life-threatening, or death). Causality with tesevatinib will be classified as: definitely related; probably related; possibly related; unlikely related; or not related. Definitely related, probably related and possibly related will be combined to related, unlikely related and not related will be combined to unrelated in some safety analyses.

The number and percentage of patients who experienced at least one TEAE as well as the number and percentage of patients who experienced AEs of each specific system organ class (SOC) and preferred term (PT) will be presented. For the presentation of AE incidences, the SOCs and the PTs within each SOC will be presented by decreasing total frequency. Tabulation by maximum severity and relationship to tesevatinib will also be included by treatment group.

The TEAEs, Grade \geq 3 TEAEs, SAEs, and TEAEs leading to dose modification/discontinuation will be summarized by treatment arm, SOC, and PT. These analyses will be repeated for events considered related (definitely related/probably related/possibly related) to tesevatinib.

Subject listings will be provided for SAEs, AEs resulting in study drug discontinuation, and deaths.

Adverse events will also be presented in listings. Time to onset and duration of AEs will be included in listings, along with action taken and outcome.

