Study data will be summarized for disposition, demographic and baseline characteristics, efficacy, and safety parameters. Unless otherwise noted, study data will be summarized by treatment group. Categorical data will be summarized by frequency distributions (number and percentages of subjects) and continuous data will be summarized by descriptive statistics (mean, standard deviation, median, minimum, and maximum). All data will be presented in subject listings.

Efficacy analyses will be based on the Efficacy Population, defined as all randomized subjects who have completed 12 months of tesevatinib or placebo treatment and have a centrally read MRI at baseline and after 12 months of treatment. The primary efficacy endpoint will be the change from baseline in htTKV at Month 12. An analysis of covariance model including treatment group as a factor and the baseline htTKV as a covariate will be used for efficacy analyses. The Type I error rate will be set at an alpha level of 0.05. Additional efficacy endpoints include change from baseline in htTKV at Months 18 and 24.

Safety analyses will be based on the modified Intent-To-Treat Population, defined as all randomized subjects who received at least 1 dose of study drug. Treatment-emergent adverse events (AEs) will be summarized using Medical Dictionary for Regulatory Activities (Version 19.0 or higher) system organ class and preferred term and presented by treatment group. Safety endpoints will include AEs and clinical laboratory evaluations (including serum creatinine, cystatin C, and calculated eGFR).

Based on the results presented in Caroli, et.al.¹ it is anticipated that the mean change from baseline in htTKV at 12 months will be 83.6 (± 90.0) mL in the placebo group. Assuming the mean change from baseline in htTKV at 12 months is 26.4 mL for the tesevatinib group, 40 subjects per group would yield approximately 80% power to detect a difference between

treatment groups based on a 2-sided t-test with a Type I error rate of 0.05. Ten additional subjects per group will be added (ie, for a total of 50 subjects per group) to adjust for drop-outs and differences in analysis methodologies (eg, the htTKV data will be log-transformed).

STUDY SCHEDULE

Table 2: Schedule of Assessments

			Early Treatment Period			End of Study ^c
Assessments	Screening ^a (-28 Days)	Day 1	Day 14 (± 1 Day)	Day 28 (± 1 Day)	Every 28 Days ^b Beginning at Month 2 (± 1 or ±3 Days)	30 Days from Last Dose (± 3 Days)

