8.3. Serious Adverse Event Collection Timeframe

All SAEs (regardless of relationship to study) are collected from the time the subject signs informed consent until the defined follow-up period stated in Table 2, and must be reported to the Pharmacovigilance vendor (see Table 1) within 24 hours of the first awareness of the event.

In addition, any SAE(s) considered "related" to the investigational product and discovered by the Investigator at any interval after the study has completed must be reported to the Pharmacovigilance vendor (see Table 1) within 24 hours of the first awareness of the event.

Serious Adverse Event Onset and Resolution Dates

The onset date of the SAE is defined as the date the event meets serious criteria. The resolution date is the date the event no longer meets serious criteria, the date the symptoms resolve, or the event is considered chronic. In the case of hospitalizations, the hospital admission and discharge dates are considered the SAE onset and resolution dates, respectively.

In addition, any signs or symptoms experienced by the subject prior to study entry or leading up to the onset date of the SAE or following the resolution date of the SAE, must be recorded as an AE, if appropriate.

Fatal Outcome

Any SAE that results in the subject's death (ie, the SAE was noted as the primary cause of death) must have fatal checked as an outcome with the date of death recorded as the resolution date. For all other events ongoing at time of death that did not contribute to the subject's death, the outcome should be considered not resolved, without a resolution date recorded.

For any SAE that results in the subject's death or any ongoing events at the time of death, the action taken with the investigational product should be recorded as "dose not changed" or "not applicable" (if the subject never received investigational product).

Regulatory Agency, Institutional Review Board, Independent Ethics Committee, and Site Reporting

Kadmon Regulatory Affairs (or designee) is responsible for notifying the relevant regulatory authorities of related, unexpected SAEs.

In addition, the Sponsor is responsible for notifying active sites of all related, unexpected SAEs occurring during all interventional studies across the tesevatinib program.

The Investigator is responsible for notifying the local IRB and the Sponsor of all SAEs that occur at his or her site as required.

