3 STATISTICAL METHODS

3.1 General Methods

3.1.1 Computing Environment

All statistical programming and data analyses will be performed using SAS® Version 9.4 on a Windows platform.

3.1.2 Sample Size Justification and power calculations:

Based on the results presented in Caroli, et.al.¹ it is anticipated that the mean change from baseline in htTKV at 12 months will be 83.6 (\pm 90.0) mL in the placebo group. Assuming the mean change from baseline in htTKV at 12 months is 26.4 mL for the tesevatinib group, 40 subjects per group would yield approximately 80% power to detect a difference between treatment groups based on a 2-sided t-test with a Type I error rate of 0.05. Ten additional subjects per group will be added (i.e., for a total of 50 subjects per group) to adjust for dropouts and differences in analysis methodologies (e.g., the htTKV data will be log-transformed).

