3.8 Treatment Exposure

Summary statistics for the duration of exposure to investigational product will be presented by treatment group. In addition, the number of dose interruptions will be provided in by-subject listings. The duration of exposure is defined as:

Duration of exposure (days) = (Date of last dose - Date of Study Day 1) + 1.

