3.9.3 Secondary Endpoint Analyses: Change from Baseline in eGFR

A secondary endpoint is the change from baseline in eGFR at months 12, 18, 24, and 30 days post-dose using the MDRD-4 formula (see Table 1).

For the 30 days post-dose endpoint, the change in eGFR from baseline to posttreatment follow-up is annualized (divided) by each subjects' treatment duration (in years). This normalization is necessary, otherwise the treatment group having more dropouts or earlier dropouts may bias the results.

At each timepoint (ie, months 12, 18, 24, and 30 days post-dose) and analysis of covariance (ANCOVA) model will be used to evaluate treatment effect. The ANCOVA model has eGFR as the dependent variable, treatment group as the factor, and baseline eGFR, patient age, and baseline htTKV as covariates.

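### Adverse events are compared as percentages of subjects treated with no allowance for time at risk, which can understate later-onset risk on tesevatinib if more of its subjects withdraw early

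*SAP*

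**What the plan says.** **Summary measure.** SAP 3.13.1 gives "The number and percentage of patients who experienced at least one TEAE" and the same by system organ class and preferred term. TEAEs, Grade 3 or higher TEAEs, SAEs and TEAEs leading to dose modification or discontinuation are tabulated by arm, and again for related events. SAP 3.2.1.2 sets the default denominator for percentages as a number of subjects. Protocol 9.11 adds the number of events. Time to onset and duration appear in listings only.

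**Exposure.** SAP 3.8: "Summary statistics for the duration of exposure to investigational product will be presented by treatment group". Nothing links that exposure to the AE tables.

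**Observation window.** Treatment lasts up to 24 months. The End-of-study visit in Protocol Table 2 falls 30 days (± 3) after the last dose and is the last scheduled point for recording AEs. Protocol 8.3 collects SAEs "until the defined follow-up period stated in Table 2", and adds that related SAEs discovered after the study must still be reported. The TEAE definition in SAP 3.13.1 has a start (first dose) but no end.

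**The SAP's own view of unequal dropout.** SAP 3.9.3 divides the 30-day post-dose eGFR change by treatment duration because "otherwise the treatment group having more dropouts or earlier dropouts may bias the results". There is no equivalent for AEs.

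**The concern.** Safety and tolerability of 50 mg QD is a secondary objective, and the AE tables are the main way the arms will be compared on it. Because observation stops soon after dosing stops, an early leaver counts fully in the denominator but has little time to contribute a later event. If leaving is more common on tesevatinib, its percentages fall for a reason unrelated to its risk.

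Drug-linked early loss is plausible, though not established at this dose. Protocol 6.7 does not allow discretionary holds in the first 28 days and requires discontinuation for severe diarrhea in that period. The amylase, QTcF and liver rules can also remove subjects. Protocol 1.3 reports rash within 28 days in 4 of 9 subjects at 50 mg.

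The point matters most for events that rest on the AE tables. Pericardial effusion is one: Protocol 6.7 names it as a concern, but SAP 3.13.5 summarises echocardiograms by valve, and Protocol 9.11 puts echocardiogram findings in listings. Ocular findings are also listings only under Protocol 9.11.

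**Working it through.** **Inputs from the documents**
- 50 subjects per arm, 1:1 (SAP 2.2, 3.1.2).
- 80 of 100 expected to complete (Protocol synopsis), so 20 expected losses. No split by arm is given.
- Completers are observed for 24 + 1 = 25 months; a subject stopping at month *t* for *t* + 1 months.

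The documents state no AE rate, so there is no AE figure to reproduce. The sample size behind the 20 losses does reproduce: a difference of 83.6 − 26.4 = 57.2 mL with SD 90 gives t-test power of 80.2% at 40 per group, and 40/0.80 = 50.

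**Assumed inputs**
- Losses of 15/50 on tesevatinib and 5/50 on placebo (total 20, as planned).
- Loss time *t* uniform on Months 0.5-2.5 (early) or 0.5-23.5 (spread).
- Constant hazard *h* of first event, equal in both arms.

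**Formula**

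Crude % = [n_stay × (1 − e^(−25h)) + n_leave × mean(1 − e^(−h(t+1)))] / 50

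**Worked case, h = 0.02 per month, early loss**
- Completer: 1 − e^(−0.5) = 39.35%. Early leaver, averaged over *t*: 4.87%.
- Tesevatinib: (35 × 39.35 + 15 × 4.87)/50 = 29.0%.
- Placebo: (45 × 39.35 + 5 × 4.87)/50 = 35.9%.
- False advantage: 6.9 points.

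**Equal true hazards, 15/5 split**

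| Hazard per month | Loss timing | Tesevatinib | Placebo | False advantage (points) |
|---|---|---|---|---|
| 2% | early | 29.0% | 35.9% | 6.9 |
| 3% | early | 39.1% | 48.2% | 9.1 |
| 2% | spread | 34.2% | 37.6% | 3.4 |
| 3% | spread | 46.2% | 50.6% | 4.4 |
| 0.2% | early | 3.6% | 4.4% | 0.9 |

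**Other splits at 2% per month.** With 12/8 the gap is (4/50) × (39.35 − 4.87) = 2.8 points for early loss. For spread loss the leaver average is 22.21%, so the gap is (4/50) × (39.35 − 22.21) = 1.4 points. With 10/10 and the same timing in both arms it is zero.

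**True excess on tesevatinib, placebo hazard 2% per month, 15/5 split**

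| True hazard ratio | Early loss | Spread loss |
|---|---|---|
| 1.3 | 35.3% vs 35.9% (hidden) | 41.7% vs 37.6% (visible) |
| 1.5 | 39.1% vs 35.9% (visible) | 46.2% vs 37.6% (visible) |
| 2.0 | 47.1% vs 35.9% (visible) | 55.8% vs 37.6% (visible) |

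**Second parameter set.** Take hazards of 0.05-0.5 per year, all withdrawals at a single month between 1 and 6, and a 30%/10% split. Under equal true hazards the crude ratio is 0.80-0.87, and the true hazard ratio that crude percentages would hide is about 1.2-1.5. The ratio of first events per person-year is 1.00 throughout.

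**What the added measure would show.** If leaving is unrelated to event risk, cumulative incidence at Month 24 with h = 0.02 estimates 1 − e^(−0.48) = 38.1% in both arms. With a hazard ratio of 1.3 it estimates 1 − e^(−0.624) = 46.4% against 38.1%.

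**The case against.** **Differential loss is not shown at this dose.** Rash-driven withdrawal is reported at 150 mg QD (3 of 5 withdrew consent in Protocol 1.3; 2 discontinuations in the Protocol 1.2 rash paragraph). The trial uses 50 mg, which the protocol calls well tolerated, and the plan expects 40 completers in each arm. This stands. The 150 mg data show a mechanism, not an expected rate, and the point is conditional.

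**The plan offers more than percentages.** Event counts, exposure by arm, reasons for discontinuation and TEAEs leading to discontinuation are all planned. Laboratory values, QTcF categories and valve results are summarised by visit. A careful reader would notice unequal withdrawal. This also stands, but none of these items corrects an AE percentage. The worst-grade laboratory shift tables in SAP 3.13.2 share the weakness.

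**Collection does not stop completely.** Related SAEs found later are reportable. That covers only related, serious events and brings no scheduled visits.

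**The larger figures need a 3:1 split, very early loss and a high hazard.** This is correct. Slow-onset events at 0.2% per month move by under half a subject in 50 (0.9% of 50), and the 95% CI for 29.0% versus 35.9% is about ± 18 points.

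**The tables are descriptive, and time-based measures have limits.** No AE test is planned. A constant rate per subject-year suits early-onset events such as rash poorly. No censoring-based measure removes bias when toxicity causes the withdrawal. These limits decide which measure to add; they do not make the crude percentage adequate alone.

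**Conclusion.** The AE comparison takes no account of time at risk in a design where observation time depends on when dosing stops. The SAP itself accepts that unequal or earlier dropout can bias a result, and adjusts for it in one eGFR analysis only. The consequence is conditional: if early withdrawal is more frequent on tesevatinib, crude percentages can understate its later-onset risks and mask modest excesses.

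On the assumed 15/5 split and hazards of 2-3% per month, the false advantage is about 7-9 points with early loss and 3-4 points with spread loss. It is under 1 point at 0.2% per month and zero with balanced withdrawal. The split, timing and hazards are assumptions; only the total of 20 losses comes from the plan.

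A reader might infer that tesevatinib would look safer on every later event, or that crude percentages are the only safety comparison. Neither is supported. A hazard ratio of 1.5 still shows as 39.1% versus 35.9% under early loss, a ratio of 1.3 shows under spread loss, and event counts and by-visit summaries are planned. The change is worth making because it is cheap and uses dates already collected; the plan's safety analysis is not invalid without it.

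**What to change.** In SAP 3.13.1:

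1. Keep the crude counts and percentages.
2. For any TEAE, Grade 3 or higher TEAEs, SAEs and the AEs the protocol names as risks (such as pericardial effusion, pulmonary and hepatic events), add by arm the cumulative incidence of first event at Months 12 and 24 with 95% CI. Measure time from first dose to first event or end of AE follow-up.
3. Optionally add first events per 100 subject-years at risk for later-onset events, but not as the main measure for early-onset events such as rash.
4. State when the TEAE window ends, and how related SAEs reported after it are shown.
5. State that neither measure removes bias from toxicity-driven withdrawal, so both should be read beside the discontinuation and exposure tables.

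**Cost.** Modest extra programming and no new data. Intervals will be wide with 50 per arm, so the added columns are descriptive.

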3.13.2 Clinical Laboratory Evaluation

The summary statistics (including number, mean, standard deviation, median, minimum, and maximum) of all laboratory variables and changes from baseline will be calculated for each visit or study assessment by treatment group. For parameters of white blood cell counts, neutrophils (absolute count), lymphocytes (absolute count),

monocytes (absolute count), hemoglobin, platelets, ALP, ALT, aspartate aminotransaminase, gamma glutamyl transferase, total bilirubin, glomerular filtration rate, plots of mean/mean changes from baseline with the corresponding standard error will be displayed.

For shift tables, laboratory results will be classified using the common terminology criteria for adverse events (CTCAE) Version 5.0. All graded laboratory parameters will be summarized separately for hematology and biochemistry. Corresponding shift tables comparing baseline to the worst post-baseline grade within the treatment period will be provided.

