- 13. Subject is taking any medication known to inhibit the cytochrome P450 (CYP)3A4 isozyme or any drugs that are CYP3A4 inducers, or any drugs associated with torsade de pointes or known to prolong the QTcF interval, including anti-arrhythmic medications within 2 weeks prior to screening. A stable regimen (≥ 4 weeks) of antidepressants of the selective serotonin reuptake inhibitor (SSRI) class is allowed (common SSRIs include escitalopram oxalate, citalopram, fluvoxamine, paroxetine, sertraline, and fluoxetine).
- 14. Uncontrolled intercurrent illness that would limit compliance with study requirements including, but not limited to ongoing or active infections or psychiatric illness.
- 15. Subject is pregnant, plans to become pregnant, or nursing.

16. Known to be positive for the human immunodeficiency virus or hepatitis B or C, as indicated by a positive test at screening.

- 17. Known to be immunocompromised.
- 18. Documented presence of renal vascular disease resulting in uncontrolled hypertension.
- 19. Has previously received an epithelial growth factor receptor (EGFR) inhibitor (including, but not limited to, erlotinib, gefitinib, osimertinib, afatinib, cetuximab, panitumumab, or an investigational agent).
- 20. Allergy or hypersensitivity to components of either tesevatinib, matched placebo, or their formulations.
- 21. Aphakic due to previous cataract surgery or congenital abnormality.

Note: The sponsor has the option to exclude a subject from enrollment, if, based upon the subject's medical history or screening results, it is felt that a subject's safety may be at risk and/or if the safety data may confound the study results.

Maximum duration of subject involvement in the study:

The planned duration of the screening period is no more than 28 days prior to dosing (42 days for MRI and ocular assessments). The planned duration of treatment period is approximately 730 days (or 24 months). The follow-up period will be 30 days from the last dose of study drug.

Endpoints and statistical analysis:

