Informed consent	>					
Medical and PKD history (include genotype, if available)	*					
Physical examination ^d (including weight)	~	~	~	~	~	~
Vital signs ^e	~	~	~	~	~	~
Supine 12-lead ECG ^f	~	~	~	~	~	~
Clinical laboratory tests ^g	~	~	~	~	~	~
Ocular evaluation ^h	>				•	>
Echocardiogram ⁱ	>			~	~	~
Pregnancy test ^j	>	~		~	~	~
MRI ^k	•				(every 6 months beginning at Month 12)	•
Randomization		~				
Study drug/placebo dispensed		~	~	*	~	>
Record adverse events	>	~	~	~	~	~
Record concomitant medication	>	~	~	*	•	>
Drug compliance/collection ¹		~	~	~	~	~

Abbreviations: ECG, electrocardiogram; MRI, magnetic resonance imaging; PKD, polycystic kidney disease; QTc(F), QT interval corrected for heart rate using Fridericia's formula; TSH, thyroid stimulating hormone

- a. Screening evaluations may be combined with Day 1 pre-treatment laboratory evaluations if both are done within 4 days before first dose of study drug. Screening MRI and ocular assessments may be performed up to 6 weeks prior to Day 1.
- b Follow-up treatment period visits to be performed monthly (every 28 ± 1 day). For those subjects continuing on study beyond 12 months, visits will occur every 2 months ± 3 days between Months 12 and 24.
- c. The End-of-study visit is to be performed 30 days (± 3 days) after last dose of study drug.
- d. A complete physical examination is to be done at the Screening and End-of-study visits. Height will only be measured at Screening. Symptom-driven physical examinations will be performed on Days 1, 14, 28, every 28 days from Months 2 to 12, and every 2 months from Months 12 to 24. See Section 7.5.1 for a description of the body systems and evaluations to be performed at each visit (eg, cardiac tamponade, ocular toxicity and xerostomia assessments).
- e. Vital sign measurements will include sitting blood pressure, heart rate, respiratory rate, and oral or tympanic temperature. On Day 1, measurements should be performed predose and 1 and 4 hours postdose. See Section 7.5.2 for details on vital signs measurement.

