If subjects experience an acute onset of new and/or progressive, unexplained pulmonary symptoms such as dyspnea, cough, and fever, study drug should be held while subjects are evaluated. If interstitial lung disease is diagnosed, study drug should be discontinued and treatment administered as necessary.

Hepatotoxicity

Rare cases of hepatic failure have been reported. Confounding factors have included pre-existing liver disease or concomitant hepatotoxic medications. Liver function test abnormalities (including elevated ALT, AST, and bilirubin) have been observed in clinical studies with tesevatinib. Interruption of study drug should be considered in subjects developing liver function abnormality $> 3 \times ULN$.

Management guidelines for liver function abnormalities are provided in Table 5.

Table 5: Management Guidelines for Liver Function Abnormalities

Liver Function Abnormality	Occurrence	Action
Hyperbilirubinemia		
$2.5 - < 3 \times ULN$	1 st	Hold dose; resume dosing when recovered or reduced to mild intensity.
	2 nd	Off study.
> 3 × ULN	1 st	Off study.
AST/ALT elevations		
2.5 – < 3 × ULN	1 st	Hold dose; resume dosing when recovered or reduced to mild intensity.
	2 nd	Hold dose and discuss management with Medical Monitor.
> 3 × ULN	1 st	Hold dose and discuss management with Medical Monitor.
	2 nd	Off study.

Abbreviations: ALT, alanine aminotransferase; AST, aspartate aminotransferase; ULN, upper limit of normal

Pericardial Effusion

Pericardial effusions have been seen in oncology studies with tesevatinib. In addition, 1 subject with ADPKD receiving 50 mg tesevatinib daily developed a trace pericardial effusion. The guidelines outlined below should be followed in the event that a subject develops a pericardial effusion while receiving tesevatinib.

For an asymptomatic pericardial effusion that is at least moderate in size, a follow-up echocardiogram should be performed within 1–3 months to monitor for progression. Results of the additional echocardiogram should be discussed with the Medical Monitor to determine subject management.

Subjects should be monitored for signs and symptoms of cardiac tamponade. In addition to the monthly to bimonthly physical exam of blood pressure, pulse, respiration, weight, heart, and lung, physical exam should also asses for tachycardia, dyspnea, neck vein distension, and edema.

Adrenal Insufficiency

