The Investigator should assess out-of-range clinical laboratory values for clinical significance, indicating if the value(s) is/are not clinically significant or clinically significant.

Abnormalities in clinical laboratory tests that lead to a change in subject management (eg, dose delay, requirement for additional medication or monitoring) are considered clinically significant for the purposes of this study, and will be recorded on the AE eCRF page.

Abnormal clinical laboratory values, which are unexpected or not explained by the subject's clinical condition may be, at the discretion of the Investigator or Sponsor, repeated until confirmed, explained, or resolved as soon as possible. If laboratory values constitute part of an event that meets criteria defining it as serious, the event (and associated laboratory values) must be reported as an SAE (see Section 8.2.3).

At the investigator's discretion, any subset of the laboratory panels in Table 6 may be duplicated in local laboratories for an immediate medical assessment. However, inclusion and

exclusion criteria as well as the final statistical analysis will be based on results from the central laboratory.

Table 6: Clinical Laboratory Tests

	Serum Chemistry		
• albumin	• BUN	 phosphorous 	
 amylase 	• calcium	• potassium	
 alkaline phosphatase 	• chloride	random glucose	
• ALT	• creatinine	• sodium	
• AST	CPK (plus CPK isoenzymes	total & direct bilirubin	
• bicarbonate	if CPK is elevated)	• total protein	
	 lactate dehydrogenase 	• magnesium	
	Hematology		
RBC count	hemoglobin	• MCV	
WBC with differential	hematocrit	• MCH	
(including neutrophils,	platelet count	• MCHC	
basophils, eosinophils, lymphocytes, monocytes)			
Tymphocytes, monocytes)			
	Coagulation	Г	
• PT	• PTT	• INR	
	Urinalysis		
• appearance	• leukocytes	occult blood (microscopic	
• color	• protein	examination of sediment	
• pH	• glucose	will be performed only if the results of the urinalysis	
 specific gravity 	bilirubin	dipstick evaluation are	
• ketones	 urobilinogen 	positive)	
Other			
Creatinine clearance ^a	• cystatin C	• TSH	
• Pregnancy test ^b	• fasting triglycerides ^c	Hepatitis and HIV ^f	
•	• lipase ^d	• HbA1c ^f	
	• amylase isoenzymes ^e		
	• CPK isoenzymes ^f		

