9.11. Safety Analyses

Safety analyses will be based on the mITT Population.

Treatment-emergent adverse events (TEAE) will be coded using the Medical Dictionary for Regulatory Activities (Version 19.0 or higher). The number of events, incidence, and percentage of TEAEs will be presented by system organ class and by preferred term for each treatment group. Treatment-emergent adverse events will be further summarized by severity and relationship to investigational product. Adverse events related to investigational product, AEs leading to withdrawal, SAEs, and deaths will be summarized/listed.

Clinical laboratory tests (including serum creatinine, cystatin C, and eGFR), vital signs, and ECG findings will be summarized by treatment group and visit. Potentially clinically important findings will also be summarized or listed.

Physical examination, echocardiogram and ocular evaluation findings will be provided in listings.

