3.13 Safety Analysis

Safety assessments will include AEs, serious adverse events (SAEs), vital sign measurements, clinical laboratory evaluations (hematology and chemistry), and

electrocardiograms (ECGs). Unscheduled visits for safety assessments will not be presented in summary tables but will be in listings. All safety analyses will be performed using the Safety Population.

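### SAP 3.13 keeps unscheduled visits out of safety summary tables and 3.13.2 makes no exception for the worst-grade laboratory shift tables, so the worst grade by arm can be understated (minor)

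*SAP*

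**What the plan says.** SAP 3.13 lists clinical laboratory evaluations (hematology and chemistry) among the safety assessments and then sets one rule for all of them: "Unscheduled visits for safety assessments will not be presented in summary tables but will be in listings".

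SAP 3.13.2 plans two kinds of laboratory output. One is descriptive statistics by visit. The other grades results by CTCAE Version 5.0 and tabulates the shift for every graded parameter: "Corresponding shift tables comparing baseline to the worst post-baseline grade within the treatment period will be provided". It does not say whether unscheduled values enter the worst grade.

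The protocol expects tests between visits. Under Clinical Laboratory Evaluations (Section 7.5), unexpected or unexplained abnormal values may, at the investigator's or sponsor's discretion, be "repeated until confirmed, explained, or resolved as soon as possible". Table 5, the liver management guideline in Section 6.7, gives this action for a first bilirubin, AST or ALT value of 2.5 to below 3 × ULN: "Hold dose; resume dosing when recovered or reduced to mild intensity".

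Scheduled laboratory tests follow Table 2: Days 1, 14 and 28, then every 28 days from Month 2. Later they are sparser: "For those subjects continuing on study beyond 12 months, visits will occur every 2 months".

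**The concern.** Leaving unscheduled values out is sensible for by-visit means, because those values belong to no visit and come mostly from subjects who already have a problem. For a table of each subject's worst grade the same rule works against the purpose, since the repeat after an abnormal result is where a higher value is most likely to be found.

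Safety and tolerability is a secondary objective. Protocol 6.7 names hepatotoxicity among the events associated with tesevatinib and reports raised ALT, AST and bilirubin in earlier studies. Protocol 9.4 plans no Data Monitoring Committee, so the final tables carry the comparison between arms. The worst-grade shift table is the planned laboratory summary of each subject's peak. If it drops repeats, a subject who is abnormal at a visit and worse on recheck is counted at the lower grade.

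**Working it through.** No power, alpha or sample size figure is at issue. The check is a reading of the rules in order, followed by the visit arithmetic.

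**1. What a programmer would do.**
- SAP 3.13: laboratory evaluations are safety assessments, and unscheduled visits are kept out of summary tables.
- SAP 3.13.2: the shift table summarizes graded laboratory results. No exception is stated.
- Result: the worst grade is taken over scheduled values only.

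**2. When the table would then be wrong.** For one subject and one parameter, let S be the highest grade among scheduled post-baseline central values in the treatment period, and U the highest among unscheduled central values in the same period. The table shows S. The true worst grade is max(S, U). The table is understated only if U > S. That happens when a recheck crosses into a higher grade than any scheduled value, or when an elevation is seen only off schedule. A recheck that confirms the grade or shows recovery changes nothing.

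**3. Whether off-schedule tests are likely.** Inputs are the Table 2 visit gaps and the general limit on dose holds in Protocol 6.7, up to 28 days and not in the first 28 days of dosing.
- Months 2 to 12: gap 28 ± 1 days. A hold starting at a visit can last until the next visit, so recovery can be checked on schedule, although resuming sooner needs an extra test.
- Months 12 to 24: gap 2 × 365.25 / 12 = 60.9 days, ± 3. A hold starting at a visit reaches the 28-day limit about 60.9 − 28 = 33 days before the next visit. Resuming on recovery therefore needs a test between visits.

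**4. Illustration of elevations that no scheduled visit would see.** The elevation lengths are assumed; the documents give none. With random onset, an elevation of d days overlaps a scheduled visit with probability min(1, d / gap).

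| d (days) | 28-day gap | 61-day gap |
|---|---|---|
| 7 | 7/28 = 25% | 7/61 = 11% |
| 14 | 14/28 = 50% | 14/61 = 23% |
| 21 | 21/28 = 75% | 21/61 = 34% |
| 28 | 28/28 = 100% | 28/61 = 46% |

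These are not rates of understatement. An elevation that misses every visit matters here only if something else prompted a central test at the time.

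**5. What the documents cannot supply.** There is no rate of ALT, AST or bilirubin elevation in ADPKD subjects and no frequency of repeat testing, so no count of affected subjects follows.

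**The case against.** **The rule may mean only that unscheduled visits get no row.** SAP 3.13 speaks of visits not being presented, and a worst grade is derived per subject. SAP 3.13.3 and 3.13.5 say outright when output is limited to scheduled time points, whereas the shift-table sentence is bounded only by the treatment period. The table shells, in a separate document (SAP Section 4), may settle it. This reading is possible, but nothing in the SAP states it, and shells that are not in hand cannot be relied on to override a rule that is.

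**Managed abnormalities reach the reader by arm anyway.** This largely stands. Protocol 7.5 requires an adverse event entry when a laboratory abnormality changes management and gives dose delay as an example. Protocol 8.1 records a change in severity as a new event. SAP 3.13.1 tabulates maximum severity, Grade ≥ 3 events and events leading to dose modification or discontinuation by arm. So it would be wrong to infer that a peak on a repeat test appears in listings only. What remains is that Protocol Table 7 grades severity by symptoms and activity while the SAP cites CTCAE, so an asymptomatic enzyme peak need not appear among the adverse events at its laboratory grade.

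**Post-treatment peaks.** A reader might infer that the SAP's undefined treatment period wrongly removes elevations after the last dose. The documents do not support treating that as an error. The protocol synopsis separates a treatment period of about 730 days from follow-up: "The follow-up period will be 30 days from the last dose of study drug". Restricting shifts to treatment is a legitimate choice, and by-visit summaries can still show the End-of-study value. Nor do the documents tie the timing of liver peaks to the drug's half-life. Only a clarification is needed.

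**Liver threshold counts.** A reader might also infer that a by-arm count of liver threshold crossings, or a peak-ALT against peak-bilirubin plot, has been wrongly omitted. Protocol 9.11 says "Potentially clinically important findings will also be summarized or listed", so a listing complies. With about 50 subjects per arm, listings can be read directly. Such outputs are a preference.

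**Conclusion.** The concern holds as a minor reporting gap. Following SAP 3.13 and 3.13.2 as written leaves unscheduled central values out of the worst-grade shift tables, so the worst grade by arm can be understated. It cannot be overstated by this route.

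The size is bounded but not estimable. The scheduled value that triggered the recheck still counts, listings hold all values, and the adverse event tables catch what changed management. Only subjects whose unscheduled grade exceeds every scheduled grade are affected.

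The conclusion assumes that a shift table is a summary table under 3.13 and that the shells do not say otherwise. It applies to all graded laboratory parameters; the liver tests are the case that matters most. It does not touch the primary htTKV result or patient management, and it does not show that liver toxicity would be concealed.

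**What to change.** Add to SAP 3.13.2, in words such as:

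> The worst post-baseline grade is taken over all central laboratory values in the treatment period, scheduled and unscheduled, as an exception to Section 3.13. The exclusion of unscheduled visits continues to apply to by-visit summaries.

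In the same place, say whether the End-of-study value, taken about 30 days after the last dose, counts toward the worst grade.

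Note one limit. Protocol 7.5 allows local duplicate tests for immediate assessment but bases the final analysis on central results. Repeats done only at a local laboratory therefore stay outside the table after this change, and the SAP should say so.

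The cost is one or two sentences and a small programming change on data already collected. No test or visit is added. A by-arm liver threshold count or a peak-ALT against peak-bilirubin plot may be added if the sponsor wishes, but the correction does not depend on either.
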